12.4.1 Definition of primary endpoint

The endpoints of primary objective are as follow:

- 1. To explore the effect of ARNI in VA events, ICD shocks and ATP.
 - 1. Paired proportion of patients by the occurrence of at least one SVT over 6 months of ACEI/ARB and 6 months of ARNI treatment
 - 2. Paired proportion of patients by the occurrence of at least one NSVT over 6 months of ACEI/ARB and 6 months of ARNI treatment
 - 3. Paired proportion of patients by the occurrence of at least one PVC over 6 months of ACEI/ARB and 6 months of ARNI treatment
 - 4. Paired proportion of patients by the occurrence of at least one ICD shocks over 6 months of ACEI/ARB and 6 months of ARNI treatment
 - 5. Paired proportion of patients by the occurrence of at least one ATP over 6 months of ACEI/ARB and 6 months of ARNI treatment

The VA event, ICD shocks and ATP assessment will be captured by ICD or CRT-D implanted into the patients.

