1.2 Purpose

The purpose of this study is to generate effectiveness data of ARNI, in the Chinese HFrEF patients with implanted ICD or CRT-D.

2 Objectives and endpoints

This study aims to explore the effect of ARNI on VA and ICD or CRT-D shocks and ATP. The objectives and related endpoints are further described in Table 2-1.

Table 2-1 Objectives and related endpoints

Objectives	Endpoints			
Primary Objective	Endpoint for primary objective			
To assess the proportion of patients with VA events over 6 months of ACEI/ARB and 6 months of ARNI treatment	Proportion of patients with VA events over 6 months of ACEI/ARB and 6 months of ARNI treatment (VA events are defined as SVT, NSVT and PVC, ICD shock and ATP, the definitions of SVT, NSVT, PVC, ATP are as below)			

Ok	pjectives	Endpoints			
Se	condary Objectives	Endpoints for secondary objectives			
•	To assess the number of occurrences of VA events and ICD or CRT-D shocks over 6 months of ACEI/ARB and 6 months of ARNI treatment	Numbers of NSVT, SVT, PVC, ICD shock and ATP experienced by patients over 6 months of ACEI/ARB and 6 months of ARNI treatment			
•	To compare the changes in LVEF and NYHA level between ACEI/ARB and ARNI treatments	 LVEF (%) over 6 months of ACEI/ARB and 6 months of ARNI treatment NYHA level over 6 months of ACEI/ARB and 6 months of ARNI treatment 			
•	To compare the changes in the NT-proBNP level between ACEI/ARB and ARNI treatments	NT-proBNP (pg/mL) level over 6 months of ACEI/ARB and 6 months of ARNI treatment			
•	To compare the healthcare resource utilization of HF patients during ACEI/ARB and ARNI treatments	Number of hospitalizations for arrhythmia or HF related hospitalizations over 6 months of ACEI/ARB and 6 months of ARNI treatment			

Abbreviations: ACEI = angiotensin-converting enzyme inhibitor;

; ARB = angiotensin receptor blockers; ARNI = angiotensin receptor neprilysin inhibitor; ATP = anti-tachycardia pacing; CRT-D = cardiac resynchronization therapy-defibrillator; HF = heart failure; ICD = implantable cardioverter defibrillator; LVEF = left ventricular ejection fraction; NSVT = non-sustained ventricular tachycardia; NT-proBNP = N-Terminal prohormone of Brain Natriuretic Peptide; NYHA = New York Heart Association; PVC = premature ventricular contraction; SVT = sustained ventricular tachycardia; VA = ventricular arrhythmias

Note

Sustained ventricular tachycardia is defined as tachycardia with hemodynamic disorder or lasting for >30 seconds

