8.3 Efficacy assessments

8.3.1 Primary efficacy endpoint

Ventricular arrhythmia events

Cardiac arrhythmia of \geq 3 consecutive complexes originating in the ventricles at a rate >100 bpm (cycle length: <600 ms). Ventricular arrhythmia events that will be measured through device to determine SVT, NSVT and PVC:

- 1. Sustained ventricular tachycardia (SVT) is defined as tachycardia lasting for ≥30 seconds or with hemodynamic disorder as determined by Holter and/or device
- 2. Non-sustained ventricular tachycardia (NSVT) is defined as recorded by Holter and/or device

3. Premature ventricular contraction is defined as an early ventricular depolarization as determined by the device, and/or detected by Holter

The proportion of patients with VA events over 6 months of ACEI/ARB and 6 months of ARNI treatment will be measured.

Anti-tachycardia pacing and implantable cardioverter-defibrillator shocks

Once VA are detected, ICD can treat with high-energy shocks or ATP. ATP consists of one or more trains of pacing stimuli, expressed as a percentage of the tachycardia cycle length for a given RR interval, from the onset of the preceding R wave.

Patients with sustained VA events will receive ICD or CRT-D shock therapy. Inappropriate shocks may occur in patients with atrial fibrillation, SVT, or other intracardiac or extra cardiac signals. An inappropriate shock is defined as a shock not delivered for VT or VF and ending if sinus rhythm was redetected by the ICD. If a subsequent episode started within 5 minutes after the previous episode ended, it was not considered as a new episode (van Rees et al 2011).

Proportion of patients had ATP, ICD or CRT-D shocks occurrence over 6 months of ACEI/ARB and 6 months of ARNI treatment will be measured.

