12.5 Analysis of secondary endpoints

12.5.1 Efficacy endpoints

Please refer to Section 2 for the secondary objectives. The corresponding secondary variables are listed below:

- 1. Paired numbers of VA (SVT and NSVT in separate), PVC, ICD and ATP over 6 months of ACEI/ARB treatment and 6 months of ARNI treatment
- 2. Change in LVEF from date of treatment initiation over 6 months of ACEI/ARB treatment and 6 months of ARNI treatment
- 3. Change of NYHA level over 6 months of ACEI/ARB treatment and 6 months of ARNI treatment
- 4. Change proportion of NT-proBNP from date of treatment initiation over 6 months of ACEI/ARB treatment and 6 months of ARNI treatment
- 5. Number of hospitalizations for all causes and HF related hospitalizations during ACEI/ARB and ARNI treatments

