12.5.2 Statistical model, hypothesis, and method of analysis

All the following analysis will be performed on the FAS and PP.

Analysis of change from date of treatment initiation after 6 months of treatment for paired quantitative endpoints

Variables involved are number of SVT experienced, number of NSVT experienced, number of hourly PVC experienced, number of ICD shocks experienced, number of ATP experienced and time duration of NSVT experienced.

For each variable, a summary table will be reported to show the changes from baseline to Month 3, and 6 post-indexing and changes from Month 6 to Month 9, and 12 post-indexing date. The changes will be summarized by mean, standard error, median, quartiles, minimum and maximum.

Amended Protocol Version 02 (Track changes)

The change from date of treatment in interested endpoint after 6 months of each treatment is calculated by taking the difference between value recorded at the date of first treatment intake and at the date of last treatment intake.

Normality will be checked for the changes calculated, if the data is parametric, paired t-tests will be performed; else if the data is non-parametric, Wilcoxon signed-rank test will be used.

Analysis of change from date of treatment initiation after 6 months of treatment for continuous endpoints

Variables involved are LVEF, NYHA and NT-proBNP.

For each variable, a summary table will be reported to show the changes from baseline to Month 3, and 6 post-indexing and changes from Month 6 to Month 9, and 12 post-indexing date. The changes will be summarized by mean, standard error, median, quartiles, minimum and maximum.

The change from date of treatment in interested endpoint after 6 months of each treatment is calculated by taking the difference between value recorded at the date of first treatment intake and at the date of last treatment intake.

Normality will be checked for the changes calculated, if the data is parametric, paired t-tests will be performed; else if the data is non-parametric, Wilcoxon signed-rank test will be used.

Other than that, the variables involved before and after the initiation of ARNI will also be analyzed using the same statistical method.

Note that NYHA is a qualitative variable, appropriate data transformation (to be described in Statistical Analysis Plan) will be used to convert it into quantitative form.

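### The primary endpoint of at least one PVC in 6 months is very likely near-saturated in both periods, has little power at most plausible rates, and is not covered by any stated PVC rate or power

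*Protocol*

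**What the plan says.** Protocol 12.4.1 lists five separate primary proportions, repeated in SAP 7.4.1. The third is "Paired proportion of patients by the occurrence of at least one PVC over 6 months of ACEI/ARB and 6 months of ARNI treatment". Each is tested by McNemar's test, with an exact binomial sign test when there are fewer than 25 discordant pairs (Protocol 12.4.2).

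On the data source, 12.4.1 says "The VA event, ICD shocks and ATP assessment will be captured by ICD or CRT-D implanted into the patients". Protocol 8.3.1 and SAP 4.1.1 are wider: "Premature ventricular contraction is defined as an early ventricular depolarization as determined by the device, and/or detected by Holter". Neither sets a minimum count or burden.

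PVC also appears as a quantity. Protocol 12.5.2 and SAP 7.4.2 include "number of hourly PVC experienced" among the secondary variables.

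The status of PVC as a VA event varies:
- Protocol Table 2-1: "VA events are defined as SVT, NSVT and PVC, ICD shock and ATP".
- Protocol 8.3.1 opens its VA description with three or more "consecutive complexes originating in the ventricles at a rate >100 bpm", then lists PVC under it. SAP 4.1.1 does the same.
- Protocol 12.5.1 sets PVC apart from VA: "Paired numbers of VA (SVT and NSVT in separate), PVC, ICD and ATP".

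The sample size section (Protocol 12.8.1, SAP 3.2.1) covers SVT and shocks only.

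**The concern.** McNemar's test learns only from patients who have the event in one period and not in the other. If one early beat in six months of device monitoring is enough, most patients are likely to be positive in both periods, whatever ARNI does to their PVC burden. A treatment that halved the burden could leave the binary outcome almost unchanged.

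At stake is the reading of one of the five primary tests. A non-significant PVC result could be reported as absence of an effect on PVC when the endpoint could hardly have registered one. The background section says a previous study found that PVC decreased, so PVC is a result that readers will look for.

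The shifting VA definition adds a smaller problem. A single beat cannot satisfy a description that requires three or more consecutive complexes, so it is unclear whether a patient with isolated PVCs has had a VA event.

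**Working it through.** **The plan's own figure.** With 8/120 on ACEI/ARB and 1/120 on ARNI for SVT:
- Discordant proportion = 0.0667 × 0.9917 + 0.0083 × 0.9333 = 0.0739; difference = 7/120 = 0.0583.
- Power of the two-sided test under the plan's rule is 0.799 at N = 174 and 0.802 at N = 175, so 175 is reproduced.
- 175 / 0.80 = 218.75, so 219 is reproduced.

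The same power calculation is now applied to PVC.

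**Inputs.** N = 175 evaluable, two-sided alpha 0.05, exact test below 25 discordant pairs and chi-square otherwise (all from the plan). Hours per period = 182.5 × 24 = 4,380. PVC rates and ARNI effects are assumed, because the documents give none.

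**Minimum evidence.** Five discordant pairs all in one direction give 2 × 0.5^5 = 0.0625; six give 2 × 0.5^6 = 0.031. At least 6 pairs are needed, which is 6/175 = 3.4% of patients.

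**Same rate in every patient.** P(at least one PVC) = 1 − exp(−rate × 4,380). With periods independent given the rate, expected discordant pairs = 175 × [p0(1 − p1) + p1(1 − p0)], where p0 is the proportion on ACEI/ARB and p1 the proportion on ARNI.

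| Rate per hour (per 30 days) | ARNI cut | p0 | p1 | Discordant pairs | Power |
|---|---|---|---|---|---|
| 0.01 (7.2) | 80% | >99.99% | 99.98% | 0.03 | about 0 |
| 0.002 (1.4) | 50% | 99.98% | 98.7% | 2.2 | 2% |
| 0.002 (1.4) | 70% | 99.98% | 92.8% | 12.7 | 99% |
| 0.001 (0.7) | 33% | 98.7% | 94.7% | 11.3 | 47% |
| 0.001 (0.7) | 50% | 98.7% | 88.8% | 21.3 | 98% |

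**Rates that differ between patients.** Let each patient's rate follow a gamma distribution with mean m and shape k, shared by both periods and halved on ARNI. Then P(no PVC in t hours) = (1 + m·t/k)^(−k), with t = 4,380 on ACEI/ARB, 2,190 rate-equivalent hours on ARNI, and 6,570 for both together.

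For m = 1 and k = 0.5, the three probabilities are 0.0107, 0.0151 and 0.0087. PVC only on ACEI/ARB: 0.0151 − 0.0087 = 0.0064. PVC only on ARNI: 0.0107 − 0.0087 = 0.0020.

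| Mean per hour | Shape | p0 | p1 | Discordant pairs | Power |
|---|---|---|---|---|---|
| 1 | 0.5 | 98.9% | 98.5% | 1.5 | 0.1% |
| 1 | 0.25 | 91.3% | 89.7% | 5.8 | 9% |
| 0.1 | 0.25 | 84.6% | 81.6% | 10.3 | 25% |

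Heterogeneity leaves more patients PVC-free, but they tend to be PVC-free in both periods. Such pairs are concordant and do not enter the test.

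**Holter alone.** With one 24-hour recording per period, 0.1 per hour and a one-third reduction, the proportions are 1 − exp(−2.4) = 91% and 1 − exp(−2.4 × 0.67) = 80%. That is not saturated.

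**The case against.** The strongest reply is that the documents report no PVC rate, so saturation is an inference. Naming an hourly count fixes a unit, not a level. If most patients had fewer than about one PVC a month, the test could work well: the first table reaches 98% and 99% power. The words allowing Holter leave open a reading in which saturation fails. All of this stands. A reader might infer that the endpoint cannot show a difference under any circumstances; the documents do not support that.

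A reader might also infer that the whole primary VA analysis saturates, because Table 2-1 places PVC inside VA. Neither document specifies a pooled test of any VA event. The five outcomes are tested separately, so SVT, NSVT, shocks and ATP are untouched. Saturation of a pooled proportion is a risk only if one is reported.

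The definition conflict, taken alone, changes no result, because PVC has its own operational definition and its own test.

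Finally, PVC burden is already analysed as a secondary variable, so no PVC information is lost. That is true, but it does not help the reading of the primary test. The burden analysis also needs tidying: SAP 7.4.2 names an hourly count yet standardizes device data per day before analysing changes.

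**Conclusion.** The concern holds in a limited form. With device capture and no burden threshold, the at-least-one-PVC outcome is very likely near-saturated in both periods. At N = 175 its power is about 0 at a uniform 0.01 per hour or more, even with an 80% reduction; about 2% at 0.002 per hour halved; and about 0.1% to 25% for a halved rate under the skewed distributions tried. It is adequate only at very low rates with a sizeable effect, or possibly under Holter-only ascertainment. The plan offers no PVC proportion, rate or power to show that the trial is in that region.

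These figures rest on assumed rates, a rate that is constant over time within each period, and independence of the two periods given a patient's rate. The inconsistent status of PVC as a VA event needs no assumption: it follows from the text.

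**What to change.** - Replace the McNemar test of at least one PVC with the within-patient comparison of PVC rate between the ACEI/ARB and ARNI periods, already planned in Protocol 12.5.2 and SAP 7.4.2. Keep the proportion as a descriptive summary, and treat the 3-month version in SAP 7.4.1 the same way.
- Use one time unit for that rate, hourly or daily, throughout SAP 7.4.2.
- State that the device is the source for the PVC measure, and align Protocol 8.3.1 and SAP 4.1.1 with 12.4.1.
- Reconcile the VA definition across Protocol Table 2-1, 8.3.1 and 12.5.1 and SAP 4.1.1, so that a single PVC does not count as a VA event. If a pooled proportion with any VA event is reported, leave PVC out of it.

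No new data are needed. The cost is procedural: an approved amendment to a primary endpoint in an ongoing open-label study, with 142 patients enrolled by 31 January 2022 and an interim efficacy analysis of 117 subjects described in SAP 3.4. The change should be dated and justified by the saturation argument, not by interim data.

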12.4.2 Statistical model, hypothesis, and method of analysis

For all primary endpoints, summaries at baseline, Month 3, 6, 9 and 12 post-indexing date will be reported together. Different hypothesis testing will be done on different types of variables as follow:

Analysis of paired patient proportions

Occurrence events to be considered SVT, NSVT, PVC, ICD shocks and ATP.

For each of the occurrence event, number of patients with at least one event stratified by treatments, will be presented in a 2 x 2 contingency table as follow:

Table 12-1 Matched pairs 2 x 2 contingency table

ARNI (case)	ACEI/ARB (control)		
	At least one event	No event	Total
At least one event	а	b	a + b
No event	С	d	c + d
Total	a + c	b+d	N = a + b + c + d

The following statistical hypothesis under 95% significance level will be tested to address the primary objective:

Null hypothesis: $p_b = p_c$ versus alternative hypothesis: $p_b \neq p_c$, where p_b and p_c is b/N and c/N respectively. The test statistic considered is McNemar Test statistic as follow:

$$\chi^2 = \frac{(b-c)^2}{b+c}$$

which has a chi-squared distribution with degree of freedom of one.

However, an exact test (binomial sign test) will be used if the discordant cells have low values (b + c < 25).

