4.1 Efficacy Endpoints

4.1.1 Primary endpoints

• Assessment of ventricular arrhythmia events

The proportion of subjects with VA events over 6 months of ACEI/ARB and 6 months of ARNI treatment will be statistically summarized.

Cardiac arrhythmia of \geq 3 consecutive complexes originating in the ventricles at a rate > 100 bpm (cycle length: < 600 ms). Ventricular arrhythmia events that will be measured through device to determine SVT, NSVT and PVC:

- 1. Sustained ventricular tachycardia (SVT) is defined as tachycardia lasting for \geq 30 seconds or with hemodynamic disorder as determined by Holter and/or device.
- 2. Non-sustained ventricular tachycardia (NSVT) is defined as recorded by Holter and/or device
- 3. Premature ventricular contraction (PVC) is defined as an early ventricular depolarization as determined by the device, and/or detected by Holter
- Assessment of anti-tachycardia pacing and implantable cardioverter-defibrillator shocks

The proportion of subjects with ATP, ICD, or CRT-D shocks over 6 months of ACEI/ARB and 6 months of ARNI treatment will be statistically summarized.

Once VA are detected, ICD can treat with high-energy shocks or ATP. ATP consists of one or more trains of pacing stimuli, expressed as a percentage of the tachycardia cycle length for a given RR interval, from the onset of the preceding R wave.

Subjects with sustained VA events will receive ICD or CRT-D shock therapy. Inappropriate shocks may occur in subjects with atrial fibrillation, SVT, or other intracardiac or extra cardiac signals. An inappropriate shock is defined as a shock not delivered for VT or VF and ending if sinus rhythm is redetected by the ICD. If a subsequent episode started within 5 minutes after the previous episode ended, it will be not considered as a new episode (van Rees et al 2011).

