7.4 Efficacy Analysis

7.4.1 Efficacy analysis of primary endpoint

The analysis will be based on the efficacy analysis set and the per protocol set.

- Proportion of paired patients who developed at least one SVT over 6 months of ACEI/ARB and 6 months of ARNI treatment.
- Paired proportion of patients by the occurrence of at least one NSVT over 6 months of ACEI/ARB and 6 months of ARNI treatment.
- Paired proportion of patients by the occurrence of at least one PVC over 6 months of ACEI/ARB and 6 months of ARNI treatment.
- Paired proportion of patients by the occurrence of at least one ICD or CRT-D shock over 6 months of ACEI/ARB and 6 months of ARNI treatment.
- Paired proportion of patients by the occurrence of at least one ATP event over 6 months of ACEI/ARB and 6 months of ARNI treatment.

Different hypothesis testing will be done on different types of variables:

Analysis of paired patient proportion

Occurrence events to be considered are SVT, NSVT, PVC, ICD or CRT-D shocks and ATP.

For each of the occurrence event, number of patients with at least one event stratified by treatments, will be presented in a 2×2 contingency table as follow:

ARNI (case)	ACEI/ARB (control)		
	At least one event	No event	Total
At least one event	a	b	a + b
No event	С	d	c + d
Total	a + c	b + d	N = a + b + c + d

Table 5-1 Matched pairs 2 × 2 contingency table

The following statistical hypothesis under 95% significance level will be tested to address the primary objective:

Null hypothesis: $p_b = p_c$ versus alternative hypothesis: $p_b \neq p_c$, where p_b and p_c are b/N and c/N, respectively. The test statistic considered is McNemar Test statistic as follow:

$$\chi^2 = \frac{\left(b-c\right)^2}{b+c}$$

which has a chi-squared distribution with degree of freedom of one.

However, an exact test (binomial sign test) will be used if the discordant cells have low values (b + c < 25).

Supportive analyses

In addition to the primary analysis, all the paired proportion will also be analyzed using the Liddell's exact test (Liddell 1983) as supportive analysis. From Table 5-1, the maximum likelihood estimate of relative risk (Mantel and Haenszel 1959), \hat{R} is given as follow:

$$\widehat{R} = \frac{b}{c}$$

Null hypothesis: $\hat{R} = 1$ versus alternative hypothesis: $\hat{R} \neq 1$ The test statistic considered, *F* is given as follow:

$$F = \frac{b}{c+1}$$

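### The primary shock item counts any ICD or CRT-D shock, and Table 2-1 calls an ICD shock a ventricular arrhythmia event, yet no visible analysis separates shocks given for VT or VF from the rest.

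*Protocol*

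**What the plan says.** Protocol 12.4.1, item 4, defines the shock outcome as "Paired proportion of patients by the occurrence of at least one ICD shocks over 6 months of ACEI/ARB and 6 months of ARNI treatment". Section 12.4.2 repeats the list without a type: "Occurrence events to be considered SVT, NSVT, PVC, ICD shocks and ATP". SAP 7.4.1 has "Paired proportion of patients by the occurrence of at least one ICD or CRT-D shock over 6 months", again for each treatment. Table 2-1 (Protocol section 2) states that "VA events are defined as SVT, NSVT and PVC, ICD shock and ATP".

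The same documents recognise two kinds of shock. Protocol 8.3.1 says "An inappropriate shock is defined as a shock not delivered for VT or VF", and SAP 4.1.1 carries the same definition. Table 8-1 lists appropriate and inappropriate shocks together as device data, and section 3 names both among the events for committee review.

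On where inappropriate shocks arise, Protocol 8.3.1 says "Inappropriate shocks may occur in patients with atrial fibrillation, SVT, or other intracardiac or extra cardiac signals"; SAP 4.1.1 says the same of subjects. The only expansion of that abbreviation in either document is the ventricular one: "Sustained ventricular tachycardia (SVT) is defined as tachycardia lasting for" at least 30 seconds, or with haemodynamic disorder.

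The supportive Liddell test (12.4.7, SAP 7.4.1) uses the same 2 x 2 table as the primary test. Sections 12.4.5 and 12.4.6 plan no sensitivity or supplementary analysis.

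For power, 12.8.1 and SAP 3.2.1 give 95%-98% for a shock difference of 0.075 at two-sided 0.05, citing published literature. They state no shock type, period rates, discordant proportion or specific N.

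**The concern.** The study asks about an effect on ventricular arrhythmia. If item 4 is read through Table 2-1, a patient shocked for atrial fibrillation or an extracardiac signal has had a VA event, although 8.3.1 says such a shock was not for VT or VF. A difference in item 4, or its absence, could then reflect either kind of shock. The type is collected, but no visible analysis uses it.

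Two smaller matters bear on this. The inappropriate-shock sentence uses SVT beside atrial fibrillation, so a site applying the documents' only definition of SVT could file sustained ventricular tachycardia as a setting for inappropriate shocks. And the shock power figure cannot be checked, because paired power depends on the discordant proportion as well as the difference.

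**Working it through.** **1. Does any rule fix the type?** Taken together, 12.4.1, 12.4.2 and SAP 7.4.1 state no type, Table 2-1 counts an ICD shock as VA, and Table 8-1 collects both types. Section 8.5 gives the committee review of device data, including shocks, and adjudication of endpoints. It does not say that an inappropriate shock leaves the count. The visible text therefore counts every shock.

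**2. The plan's own sample size (SVT).** Inputs from 12.8.1: 8/120 on ACEI/ARB (Pt) and 1/120 on ARNI (Ps).
- Discordant proportion pd = Pt(1-Ps) + Ps(1-Pt) = (8 x 119 + 1 x 112)/14,400 = 0.0739, as stated.
- Difference d = 7/120 = 0.0583 in absolute value, as stated.
- Power: the number of discordant pairs M is Binomial(N, pd). Given M, the number with an event on ACEI/ARB only is Binomial(M, (pd+d)/(2pd)). The planned rule is applied: exact sign test if b+c<25, otherwise chi-square.
- Result: 0.802 at N=175. Then 175/0.80 = 218.75, so 219. Both figures reproduce.

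**3. The shock power.** With only d = 0.075 given, pd is unknown and the 95%-98% cannot be reproduced. The ARNI-period rates below are assumptions. The ACEI/ARB rate is that rate plus 0.075, and pd follows the plan's independence formula.

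| ARNI rate (assumed) | pd | Power, N=175 | Power, N=219 |
|---|---|---|---|
| 0 | 0.0750 | 99.2% | 99.9% |
| 1/120 | 0.0903 | 93.1% | 97.7% |
| 2% | 0.1112 | 84.0% | 92.4% |
| 4% | 0.1458 | 73.0% | 84.9% |

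With chi-square throughout, the 1/120 row becomes 95.8% and 98.7%. Under the planned rule, power reaches 95% only if the ARNI rate is at most 0.60% at N=175 or 1.44% at N=219. With a within-patient correlation of 0.5 those limits rise to 4.4% and 6.5%.

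**4. Can dilution by inappropriate shocks be sized?** Assume 0.075 refers to appropriate shocks only (10/120 vs 1/120), which gives 93% at N=175, and add inappropriate shocks at assumed rates:
- equal rates of 1% to 6% per period: 85% down to 59% (independent periods), or 91% down to 81% (correlation 0.8);
- rates halved on ARNI (2% to 1%, 4% to 2%, 6% to 3%): 91%, 91% and 92%.

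If 0.075 is already an all-shock difference, this loss does not arise. The answer is set by the assumption, so no size can be claimed.

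**The case against.** The strongest case is that shocks are an outcome in their own right. Section 2, the clinical question in 2.1, and 12.4 name shocks and ATP beside VA. Section 8.3.1 and SAP 4.1.1 put them under a separate heading, and SVT and NSVT have their own primary tests. Only the Table 2-1 parenthesis merges shocks into VA. An any-shock count is a valid device-therapy outcome and needs no judgement of type. This stands, and it is why item 4 should not be replaced.

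A reader might infer four stronger things that the documents do not support.
- *That the primary test should become appropriate shocks only.* Treatment is open to assessors (6.4), so sites would partly decide what counts. The change would also fall around an interim efficacy analysis of 117 subjects (SAP 3.4). That trade-off is debatable, and a supportive test meets the need.
- *That the 95%-98% is wrong.* It is attainable under the plan's own SVT rate for ARNI, and the sample size does not depend on it. It is only uncheckable.
- *That only uncertain events are adjudicated.* Section 8.5 routes uncertain events to subgroup 1, but it does not say only those, and it also gives the committee shock review and endpoint adjudication.
- *That the SVT sentence strictly contradicts the definition.* It says where such shocks may occur; the definition is the next sentence. The ambiguity remains, but it alters no test.

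Section 8.3.1 also says that the device can treat VA once detected, which might suggest an intent to count ventricular therapy only. No counting rule follows from it. Finally, sections 8.3.3 and 12.6 are not in the public text, so an analysis by shock type there cannot be excluded.

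**Conclusion.** The point holds as a gap in interpretation. Followed as written, item 4 together with Table 2-1 counts a non-ventricular shock as a VA event, and no visible analysis separates the types. The any-shock test is computable and legitimate, but by itself it cannot carry a conclusion about ventricular arrhythmia. The effect on power or on the estimate is unknown, because the documents give no inappropriate-shock rate. The missing basis for the shock power is a minor reporting matter. The figures given for it rest on assumed ARNI-period rates and, except where a correlation is stated, on independent periods.

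**What to change.** 1. Keep the any-shock McNemar test as primary item 4.
2. In Protocol 12.4.7 and SAP 7.4.1, add the same paired test for at least one appropriate (VT/VF) ICD or CRT-D shock, with inappropriate-shock counts per period. Use the type already collected under Table 8-1, with the committee's classification prevailing where it reviewed the event.
3. State that any conclusion about ventricular arrhythmia drawn from shocks rests on the appropriate-shock result. Limit the ICD shock entry in the Table 2-1 VA definition to appropriate shocks; item 4 then stands as a device-therapy outcome.
4. In 8.3.1 and SAP 4.1.1, spell out the rhythm meant by SVT in the inappropriate-shock sentence.
5. Reporting only: in 12.8.1 and SAP 3.2.1, give the shock type, both period rates and the N behind 0.075 and 95%-98%.

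The cost is a protocol amendment (14.1) and a SAP revision, with no new data. There are two downsides. Shock type is partly judged by open-label sites. The analysis would also be added after enrolment began (142 patients by 31 January 2022), which could look data-driven. So record the date of the change relative to the interim analysis, and show the any-shock and appropriate-shock results side by side.
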